6.2. Patient Management

All patients must provide written informed consent before the performance of any study-related procedure. Patients eligible for the study will be randomized into the study 0-3 days prior to Day 1 and will receive a total of 6 IV infusions of study drug (either ATYR1923 or placebo) administered once every 4-weeks, according to their treatment assignment on a double-blind basis. Patients will attend a post-treatment follow-up visit 4 weeks after completion of dosing.

6.3. Patient Adherence

All patients are required to adhere to the protocol-specified dosing and visit schedules. If a patient misses a scheduled visit, attempts should be made to reschedule the visit within the visit windows specified in Table 1. Failure to attend scheduled study visits may result in discontinuation from the study.

39

6.3.1. Study Conduct During the COVID-19 Public Health Emergency

Note that due to the coronavirus disease-2019 (COVID-19) public health emergency, it is understood that some flexibility may be required around the timing of scheduled study visits beyond the visit windows specified in the Schedule of Assessments (Table 1). In particular, the 4-week Screening period may be extended to 6 weeks, laboratory or clinical tests may be performed locally, and telephone contacts may be utilized to follow patients with delayed or missed study visits.

Patients missing 2 consecutive study drug doses are to have study drug permanently discontinued, complete the EOS visit, and be withdrawn from the study. (Patients who withdraw from the study due to COVID-19-related issues may be replaced; see Section 6.4.3.

Note that COVID-19 screening is not required per protocol; however, each study center is to follow standard institutional practice regarding COVID-19.

All deviations due to COVID-19 are to be documented.

6.4. Withdrawal and Replacement of Patients

6.4.1. **Study Drug Discontinuation Criteria**

Study drug must be discontinued if any of the following events occur:

- A serious adverse event (SAE) during or within 60 minutes of IV infusion that includes cardiac and/or respiratory observations, that has a reasonable possibility of a causal relationship with the study drug, including a severe IRR.
- Pregnancy.
- Patient request to discontinue study drug dosing for any reason.
- Other findings that, at the discretion of the Investigator and/or Sponsor, indicate that study drug administration should be discontinued.
- Missing 2 consecutive study drug doses.

The Investigator has full discretion to stop study drug infusion at any time, if clinically warranted or in the patient's best interest.

All patients who have been dosed with any amount of study drug will continue to be followed for safety. Patients who discontinue study drug dosing at any time during the treatment period should return to the study center for the EOS visit and as clinically indicated. Patients who have skin lesions that are being followed and withdraw from the study prior to Week 12 will be asked to have a skin biopsy at the EOS Visit. If applicable, patients who withdraw from the study prior to Week 16 will be asked to have a ¹⁸F-FDG-PET/CT at the EOS Visit.

Patients who decide not to receive any further study drug will be offered all follow-up safety assessments, including the EOS visit after their last infusion.

If a patient fails to attend scheduled study assessments, the Investigator must determine and document the reasons and the circumstances as completely and accurately as possible.

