9.9. Management of Potential Infusion Related Reactions, Including Anaphylaxis

ATYR1923 is a biologic and as with all biologics there is a risk for IRRs. These reactions typically occur in close temporal relationship with the infusion. They may be related to cytokine release or immune mediated.

A generalized IRR could be occurring when any symptoms begin during the study drug infusion or during the post-infusion observation period. While these symptoms may be self-limiting, such symptoms may signal the possibility of a severe reaction that could escalate into a life-threatening situation.

66

Should a patient develop an IRR the subsequent management will depend on the nature of the IRR. Where the IRR symptoms are not cardiorespiratory in nature i.e. they comprise cutaneous rash, flushing, burning sensation etc. and are mild to moderate in intensity – the patient may complete the infusion and receive subsequent doses. The patient will need to be observed until all symptoms resolve or for 6 hours after the end of the infusion. Subsequent dosing should continue to occur in a facility where the patient can be monitored closely. The Investigator, in consultation with the Medical Monitor, may opt to adjust the infusion duration and/or administer pre-medication (antihistamines, non-steroidal anti-inflammatories and anti-emetics) if clinically indicated, although this is not mandatory.

If the IRR symptoms constitute a cardiorespiratory risk (hypotension, dyspnea, hypoxia etc.) or any severe AE then all further dosing should be stopped for the patient. If necessary, the patient should be transferred to an acute care facility.

Once the patient is stabilized, additional blood samples are to be collected and procedures performed as outlined below:

• Vital signs, pulse oximetry, infusion site examination, and ECGs are to be performed to gather clinical information as soon as possible after the onset of clinical symptoms of a generalized IRR (for instance, immediately after cessation of the study drug infusion if such a reaction is seen). Vital signs are to be monitored as medically indicated and pulse oximetry is to be monitored continuously for at least 2 hours or until the patient has recovered, whichever is longer. ECGs should be repeated as medically indicated.

Once medical treatment of the IRR has begun, blood samples are to be obtained for assessment of:

- Plasma complement factors (C3a, C4a, C5a, Bb, SC5b-9).

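### Protocol Sections 6.4.1 and 9.9 set different thresholds for permanently stopping study drug after an infusion reaction, and 9.9 is the broader of the two

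*Protocol*

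**What the plan says.** Protocol Section 6.4.1 opens its list with "Study drug must be discontinued if any of the following events occur". The entry that bears on infusion reactions is "A serious adverse event (SAE) during or within 60 minutes of IV infusion that includes cardiac and/or respiratory observations", and it continues "that has a reasonable possibility of a causal relationship with the study drug, including a severe IRR". A later entry in the same list is a catch-all: "Other findings that, at the discretion of the Investigator and/or Sponsor, indicate that study drug administration should be discontinued".

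Protocol Section 9.9, on managing infusion-related reactions, has its own stopping rule: "If the IRR symptoms constitute a cardiorespiratory risk (hypotension, dyspnea, hypoxia etc.) or any severe AE then all further dosing should be stopped". It treats a generalized IRR as possible when "any symptoms begin during the study drug infusion or during the post-infusion observation period". It allows the infusion to be completed and later doses to be given only where the symptoms are both non-cardiorespiratory and mild to moderate.

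Section 9.9.1 sends anaphylaxis to 9.9 for management. Neither 6.4.1 nor 9.9 refers to the other on when to stop dosing.

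**The concern.** Two sections of one protocol answer the same question with different conditions: after an infusion reaction, does this patient receive another dose? Section 6.4.1 carries the title under which a site would look for discontinuation criteria, and it has the narrower trigger. Section 9.9 is the section on managing reactions, and it has the broader one.

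The first stake is patient safety. Section 9.9 names infusion reactions as a risk of this biologic and warns that early symptoms may precede a severe reaction. Every patient enters with dyspnea (modified MRC grade 1 or more, Section 5.1.1), so respiratory symptoms around an infusion are foreseeable. A site relying on 6.4.1 alone could give a further dose to a patient whom 9.9 would stop.

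The second stake is the data. TEAEs leading to study drug withdrawal are a line in the overall TEAE summary (SAP Section 9.1). Stopping can also decide whether a patient reaches the four doses needed for the Efficacy Evaluable Set (SAP Section 7.1.3) or the five of six doses needed to count as a completer (Protocol Section 6.5).

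**Working it through.** No sample-size, power or other calculated figure is involved, so the check is a comparison of conditions applied to the same hypothetical patients.

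| Condition | Section 6.4.1 | Section 9.9 |
|---|---|---|
| Strength of wording | *must* | *should* |
| Seriousness | SAE required | not required |
| Severity | severe IRR mentioned, but inside the SAE entry | any severe AE is enough |
| Symptom type | cardiac and/or respiratory observations | cardiorespiratory risk, or any type if severe |
| Timing | during or within 60 minutes of infusion | during infusion or the post-infusion observation period, length not defined |
| Causality | reasonable possibility | not stated separately; the event is taken to be an IRR |
| Other cases | Investigator and/or Sponsor discretion | may continue only if non-cardiorespiratory and mild to moderate |

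Seriousness and intensity are separate in this protocol. Section 9.1.3 defines seriousness by outcome, while Section 9.2 grades intensity. A Grade 2 event need not be an SAE.

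Applying both rules:

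1. **Non-serious Grade 2 dyspnea during the infusion, judged a cardiorespiratory risk.** Section 9.9 stops all further dosing. In 6.4.1 the event is neither an SAE nor a severe IRR, so no mandatory criterion is met. The rules differ, and this does not depend on any ambiguous wording in 6.4.1.
2. **Cardiorespiratory reaction starting more than 60 minutes after the infusion.** If it starts within the observation period, 9.9 stops dosing. The 6.4.1 entry fails on timing, even if the event is serious. The rules differ only if the observation period runs past 60 minutes, and its length is not given.
3. **Severe (Grade 3), non-serious, purely cutaneous reaction.** Section 9.9 stops dosing because the event is severe. If a severe IRR in 6.4.1 is read as part of the SAE entry, that entry is not met and the rules differ. If it is read as a stand-alone trigger, they agree.
4. **Drug-related respiratory SAE during the infusion.** Both stop.
5. **Mild to moderate cutaneous reaction.** Neither requires stopping.

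I found no reaction that must stop under 6.4.1 but may continue under 9.9. The mismatch runs one way. Case 1 establishes it; cases 2 and 3 add to it only on one reading of unclear text.

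**The case against.** The best defence is that the two sections can be obeyed together. The 6.4.1 list gives events that are sufficient for stopping and does not claim to be complete. Its discretionary entry can accommodate any stop made under 9.9. Section 9.9 also requires the Investigator to inform the Medical Monitor promptly of any generalized IRR for further instruction, which gives a central check on how sites act.

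This stands in part. A reader might infer that sites receive opposite instructions. The documents do not support that: 6.4.1 nowhere tells a site to continue dosing after a reaction, and 9.9 says *should*, so it is also too strong to say a patient must stop under 9.9. But permission to stop is not a requirement to stop. Contact with the Medical Monitor reduces divergence between sites without saying which threshold governs.

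Two numerical readings are also tempting and do not hold.

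- A reader might take the vital-sign schedule, which runs to 4 hours after the start of infusion, as the observation period and work out how much of it lies outside the 60 minutes in 6.4.1. The protocol does not equate the two. The 6-hour observation in 9.9 applies to a patient who has already had a milder reaction, so it does not define the period either.
- A reader might size the effect as one of the 8 active patients in a cohort. That fraction would apply to any event in an arm of that size and says nothing about how often the sections would disagree.

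On frequency, Section 2.2 reports no definitive IRR among 25 healthy subjects given ATYR1923, with one that could not be ruled out. Those were single doses, so the reassurance for repeated dosing in patients is limited.

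**Conclusion.** The inconsistency is real and of moderate severity. It is a fault in the protocol's wording, not a design choice. For a non-serious, non-severe IRR whose symptoms are judged a cardiorespiratory risk, 9.9 directs that dosing end while 6.4.1 leaves the matter to discretion. Whether symptoms amount to such a risk is itself a clinical judgement.

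Two further differences are conditional. Late-onset reactions depend on the undefined observation period. Severe but non-serious reactions depend on whether a severe IRR in 6.4.1 must also be an SAE.

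The practical size cannot be estimated from the documents. The effect on reported results is limited. The primary endpoint is the incidence of TEAEs and SAEs, withdrawals due to TEAEs are one descriptive line beneath it, and no formal hypothesis testing is planned. A stop after the fourth dose still meets the dose requirement for the Efficacy Evaluable Set, and a stop after the fifth still meets that for completion. The main reason to act is that a patient could be re-exposed under one section whom the other would stop.

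**What to change.** Reconcile Sections 6.4.1 and 9.9 on five items:

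- whether seriousness, severity or either triggers stopping;
- which symptom types count;
- the time window and the point it is measured from;
- the length of the post-infusion observation period;
- whether a severe IRR is a trigger in its own right.

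State the resulting rule once and have the other section refer to it. Use the same strength of wording in both places. Which criteria apply is for the sponsor and its medical and safety advisers to decide; this review takes no position on it.

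The cost is a wording change to two protocol sections. It needs no extra visits, assessments, staff or patients, and the SAP tables stay as they are.

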6.4.2. Study Withdrawal Criteria

Patients will be informed that they have the right to discontinue from the study and withdraw consent at any time for any reason, without prejudice to their medical care. The Investigator also has the right to withdraw patients from the study for any of the following reasons:

- Patient non-adherence to study drug or protocol requirements.
- Patient unwillingness to continue in the study.
- Any other reason, based upon the medical judgment of the Investigator.

The reason for study withdrawal is to be documented in the patient's source documents and eCRF.

At the time of discontinuation from the study, patients are to have all the assessments planned for the final follow-up visit performed after the last study drug dose, if feasible.

6.4.3. Replacement of Patients

If a patient is withdrawn from the study for any reason, whether related to the study drug or not, or if a patient voluntarily withdraws before or after receiving the study drug, such patient will be considered an early-termination patient.

Investigator will make every effort to ensure that early-termination patients who have received study drug complete the safety follow up assessments.

Patients who withdraw for reasons other than treatment-related AEs may be replaced at the discretion of the Sponsor. The decision regarding the replacement of patients will be documented.

6.5. Study Completion

A patient is considered to have completed the study if they received at least 5 of 6 scheduled study drug doses and completed all follow-up visits.

6.6. Study Termination

If the Sponsor or Investigator discovers conditions arising during the study that suggest the study should be halted, then this can happen only after appropriate consultation between the Sponsor and Investigator. Conditions that may warrant study termination include, but are not limited to:

- The discovery of any unexpected, significant, or unacceptable risk to the patients enrolled in the study.
- Insufficient adherence to the protocol requirements.
- A decision on the part of the Sponsor to discontinue the Study
- A decision on the part of the Sponsor to suspend or discontinue development of ATYR1923.

6.7. Investigator Compliance

If the study center deviates significantly from the protocol without prior approval from the Sponsor and regulatory authorities, the center may be discontinued from the study. The Investigator is responsible for ensuring the accuracy and completeness of all research records, the accountability of Study Drug, and the conduct of clinical and laboratory evaluations as outlined in the protocol. The Investigator is responsible for ensuring that the clinical study is performed in accordance with the Declaration of Helsinki and the International Council for Harmonisation (ICH) Good Clinical Practice (GCP) guidance documents.

6.8. Data Safety Monitoring Board

Ongoing review of blinded safety and tolerability data will be performed by the Medical Monitor and aTyr Pharma personnel.

In addition, an independent DSMB will perform interim reviews of unblinded safety, tolerability, and immunogenicity data from each cohort and hoc per Sponsor request if a pattern of unexpected, clinically significant trends or changes in other safety assessments is identified through blinded safety data reviews.

The DSMB will provide its recommendation to aTyr Pharma. Such recommendation may include, but is not limited to: stopping an ongoing cohort, stopping further dose escalation, continuation of the study as planned, or continuation of the study with modifications, such as evaluation of a lower or intermediate dose in the next cohort(s) to gain more information on safety and tolerability.

7. STUDY DRUG

7.1. Study Drug Dose and Administration

7.1.1. Treatments Administered

The planned study cohorts are identified in Table 2. In all study cohorts, it is planned that study drug will be administered as an IV infusion over approximately 60 minutes every 4 weeks for a total of 6 doses (20 weeks of treatment). Within each cohort, patients will be assigned to ATYR1923 or placebo according to the computer-generated randomization list (see Section 7.1.3).

Although this is an escalating dose study, if safety or tolerability issues are experienced, or the actual ATYR1923 PK appears to be substantially different from what is predicted, a different dose or interval may be administered in the next cohort. Further, an intermediate dose may be tested to gain more information on safety, tolerability and/or PK.

For the preparation of the ATYR1923 dose levels, the patient's weight at Screening will be used.

7.1.2. Identity of Investigational Products

7.1.2.1. **AYTR1923**

The ATYR1923 Drug Product is a sterile, clear to slightly opalescent, colorless to slightly yellow, preservative-free liquid concentrate for IV administration. ATYR1923 Drug Product (3.8 mL fill volume) is supplied in a single-use borosilicate glass vial, stoppered with bromobutyl rubber stopper (with FluroTec coating), and sealed with aluminum Flip-off® seal. The formulation of ATYR1923 Drug Product contains 25 mg/mL ATYR1923, 20 mM L-histidine, 125 mM sodium chloride, 3% sucrose, 10 mM L-methionine, and 0.02% polysorbate 20 at pH 6.9.

ATYR1923 will be administered to patients by IV infusion after appropriate dilution in 0.9% sterile sodium chloride solution, United States Pharmacopeia (USP) as outlined in the study Pharmacy Manual.

7.1.2.2. Placebo

Placebo will be supplied as the formulation buffer in vials that are similar in appearance to ATYR1923.

Placebo will be administered to patients by IV infusion after appropriate dilution in 0.9% sterile sodium chloride solution, USP, as outlined in the study Pharmacy Manual.

7.1.3. Method of Assigning Patients to Treatment Cohorts

After obtaining informed consent, patients will be screened according to the inclusion and exclusion criteria and will be assigned to a cohort based on their availability. Within each cohort, 12 patients will be randomized 2:1 (block size of 6) in a blinded fashion to ATYR1923 (N=8) or placebo (N=4).

7.1.3.1. Dose Escalation Procedure

Cohorts 1 through 3 will be enrolled sequentially in a staggered manner. After at least 6 patients of a given cohort have received at least 3 infusions of study drug (ATYR1923 or placebo), cumulative unblinded safety data (including but not limited to any reported AEs, ECG recordings, clinical laboratory tests, and vital signs) will be reviewed by the DSMB. Enrollment in the next scheduled cohort may commence after this review is completed, dose escalation is approved, and the remaining 6 patients have been randomized in the previous cohort. Dose escalation will continue in this manner until the highest planned dose level of ATYR1923 is reached, or the criteria for pausing enrollment have been met (see Section 7.1.3.2).

7.1.3.2. Criteria for Pausing Enrollment

In the event that a serious unexpected suspected adverse reaction (SUSAR) has occurred, the enrollment and initiation of study drug administration to new patients will be paused and the Sponsor will request an unblinded review by the DSMB, who will provide its recommendation to aTyr Pharma. Such recommendation may include, but is not limited to, stopping an ongoing cohort, stopping further dose escalation, continuing the study as planned, or continuing the study with modifications, such as evaluation of a lower or intermediate dose in the next cohort(s) to gain more information on safety and tolerability.

In addition, if unexpected, clinically significant trends or changes in other safety assessments are identified during routine blinded safety reviews the Sponsor may request the DSMB to similarly perform an unblinded review and provide recommendations.

7.1.4. Selection of Doses in the Study

7.1.4.1. First-in-Human Study ATYR1923-C-001

The first in human study ATYR1923-C-001 evaluated single ascending dose administration of ATYR1923 at doses of 0.03, 0.1, 0.3, 1, 3.0 and 5.0 mg/kg.

The ATYR1923 starting dose of 0.03 mg/kg was based on: 1) the no-observed adverse effect level (NOAEL) from non-clinical Good Laboratory Practice toxicity studies;

2) estimation of the human minimum pharmacologically active dose (PAD) level range (0.035 to 0.1 mg/kg) based on total body weight; and 3) estimation of human PAD based on predicted ATYR1923 human serum PK parameters, determined from single species (NHP) allometric scaling to humans. These approaches supported a human starting dose level for ATYR1923 of 0.03 mg/kg, which was just below the lower end of the human PAD calculation range (0.035–1.0 mg/kg) and well below the maximum recommended starting dose (0.97 mg/kg). The highest single dose (5.0 mg/kg) planned in the first-in-human Phase 1 study was anticipated to produce mean serum exposure levels that remained at least 2-fold below those seen in animal toxicity testing at the NOAEL.

7.1.4.2. Current Study in Patients with Pulmonary Sarcoidosis

The proposed doses in the current study in patients with pulmonary sarcoidosis are 1.0 mg/kg (Cohort 1), 3.0 mg/kg (Cohort 2), and 5.0 mg/kg (Cohort 3). Cohorts will be enrolled sequentially in a staggered manner.

Selection of the proposed doses is primarily informed by clinical and pharmacological findings from ATYR1923-C-001, in which single doses of ATYR1923 were well tolerated across the broad dose range from 0.03 up to 5.0 mg/kg, with no clear dose-relationship with regard to the incidence of TEAEs, or changes in clinical laboratory parameters or other safety measures. No SAEs or severe AEs were reported at any dose, indicating that the starting dose of 1.0 mg/kg dose in this study should be acceptable.

Repeat administration of ATYR1923 once monthly is expected to result in little or no accumulation of peak (ie, maximum concentration [C_{max}]) and total (ie, area under the curve [AUC]) serum exposure measures at steady-state when compared to single dosing. For example, C_{max} and area under the curve from time zero to 168 hours (AUC[0-168h]) after the 6th monthly dose of ATYR1923 at 5 mg/kg is predicted to be 109,618 ng/mL and 3,577,275 ng·h/mL, respectively; estimates that are highly similar to the values observed after a single dose of ATYR1923 at 5 mg/kg in ATYR1923-C-001 (109,250 ng/mL and 3,417,001 ng·h/mL, respectively).

In a Good Laboratory Practice-compliant 6-month duration toxicology study in NHPs, the NOAEL was 60 mg/kg by IV injection once weekly, the highest dose administered. The mean serum exposures (AUC_[0-168h]) measured at the NOAEL in this study ranged from 27,900,000 ng·h/mL (Day 1) to 44,400,000 ng·h/mL (Day 176). Comparison of the mean serum exposures observed in NHPs with those predicted in subjects after the 6th monthly dose of ATYR1923 at the 5 mg/kg dose (3,577,275 ng·h/mL) estimates a safety margin of 8-12-fold. Safety margins based on comparison of mean maximal concentrations (mean C₀ ranged from 1,880,000-2,080,000 ng/mL in NHPs versus the mean predicted C_{max} of 109,618 ng/mL in humans) are higher at 17-19-fold. Therefore, repeat-dose administration of ATYR1923 to patients over a 6-month duration at doses up to 5 mg/kg is expected to produce mean serum exposures that remain well below those seen in animal toxicity testing for up to 6 months.

